We will use a prospective, randomized, experimental design to accomplish the specific aims. Subjects (n=182) will be randomly assigned within 48 hours of intubation and ICU admission to one of two groups. The intervention group will receive the FAVoR intervention over a 5-day period (120 hours) or until discharge from the ICU, if discharged within 5 days. The control group will receive standard ICU care, but will not receive the FAVoR intervention. All subjects will receive standard clinical care for mechanically ventilated patients, as per clinical guidelines and clinical agency guidelines. Standard clinical care includes all components of the IHI ventilator care bundle.³⁷

Sample. Because delirium occurs with a greater frequency in those who are mechanically ventilated,⁴³ this study will focus on subjects who are mechanically ventilated. The sample of 182 subjects will be drawn from all patients over the age of 18 years admitted to the Intensive Care Units at University of Miami Hospital (UMH) and Jackson Memorial Hospital (JMH) who are newly intubated (within 48 hours of initial intubation at time of study recruitment) and have a family member available to record the scripted intervention message. Subjects will be randomized to group according to a permuted block design⁴⁴ developed by [name] such that after every k subjects, balance will be maintained between the groups. In order to fully enroll the study during the requested 4-year funding period, we will target enrollment of 7 subjects per month.

Group Assignment. The Project Director and Research Assistants will recruit, enroll, and assign subjects to groups. Subjects will be randomly assigned to one of two study groups (FAVoR intervention or control) using randomization processes described in the Sample section above.

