Each message indicates that it is daytime (to provide general time orientation), states that the message is a recorded message, and tells the subject that he/she will hear messages frequently throughout the day to help him/her understand that he/she is in the ICU. Other than the patient's name, the recorded message is generic in nature, and not specific to any one patient condition, procedure, or family situation. Topics for message scripts were developed in response to patients' recollections of the ICU experience.³⁸⁻⁴⁰ The 8 recorded messages will vary randomly in order each day, reducing message repetition, which may eventually annoy or be ignored by the subject.

The messages will be recorded by a family member of the family's choice using a standardized script, in either English or Spanish, based on the family member's decision regarding which language would be most meaningful to the subject. Family members are not human subjects in this project; no data will be collected about the family members. The messages will be digitally recorded using audacity software and stored on the study computer's hard drive as a standard Microsoft wave files. The wave files are loaded onto a small, wireless, digital audio player with a wireless speaker, protected inside a disposable plastic bag, placed near the subject's ear, and set to shuffle play. Shuffle play is a mode of audio playback in which messages are played in a randomized order that is decided upon for all tracks at once and prevents repeated tracks, which makes it distinct from random playback. Shuffle play randomly selects the order of the messages to be played in the patient's room every hour for 8 hours during the daytime, beginning at 9:00 am. The digitally recorded messages will continue at the predetermined daytime intervals each day for a total of 5 days (120 hours), or until ICU discharge if ICU discharge occurs prior to 5 days. All intervention "doses" will be administered during the hours of 9:00 am and 4:00 pm for each of the 5 days, with intervention beginning at the earliest available time following completion of family recording. The research personnel will document the time and number of recordings each day so that a message "dose" can be documented. Research personnel will monitor the subject and the recorded messages regularly to document if the subject was not in the unit (for procedures off the unit etc.) so that those off-unit times can be included in the dose calculation.

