3. SP-PSG (substituted by PROMIS-SD and PROMIS-SRI)
4. NIH Toolbox Cognition Battery (substituted by PROMIS-CF and PROMIS-CFA)

Delirium. The primary outcome measure for this project is delirium free days. We will quantify delirium using the Confusion Assessment Method for the ICU (CAM-ICU).⁴⁵ CAM-ICU scores for each subject will be obtained by study personnel twice daily at 9 am and 4 pm (coinciding with the schedule for initiation and conclusion of messages each day in the FAVoR intervention group, and at identical times for the control group). CAM-ICU scores will also be recorded at the same times for two days following the completion of the intervention period. The Confusion Assessment Method (CAM) will be used during study visits after transfer from the ICU (post ICU, 1 month, and 6 month follow up periods) for comparison.

We will also collect documentation by providers in the medical record of episodes of delirium occurring outside of the CAM-ICU data collection conducted by research personnel. Only days without any instances of delirium will be counted as delirium free days. The CAM-ICU is recognized in the Clinical Practice Guidelines for the Management of Pain, Agitation, and Delirium in Adult Patients in the Intensive Care Unit as a valid, reliable, and feasible tool to detect delirium in ICU patients³ with pooled sensitivity of 75.5% and specificity of 95.8%.⁵⁰

Sleep/Activity. Sleep patterns in the critically ill are highly disorganized, with fragmentation, a predominance of light sleep, and reduction in deep sleep and rapid eye movements.⁸ We will use the FDA approved Sleep Profiler system (Advanced Brain Monitoring, Carlsbad, CA) to obtain continuous polysomnography data (SPPSG). The Sleep Profiler has been successfully utilized in mechanically ventilated and sedated patients and provides three frontopolar electroencephalographic (EEG) signals (AF7/AF8, AF7/Fpz and AF8/Fpz).⁵¹⁻⁵⁴

A wrist actigraph (ActiWatch Spectrum, Philips Respironics, Bend, OR) will be placed on the wrist to measure patient activity and ambient light levels. We have extensive experience with

IRB Study Number: 20170771, Version #1.8, Date: 03/10/21, PI: [name]

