Inpatient. Once consent is obtained and the subject is enrolled, baseline data will be collected from medical records. In randomized assignment to the intervention group, the family member selected by the family to record scripted FAVoR messages will be contacted, and taken to a quiet area to complete the recording on the assigned computer. FAVoR will be delivered through a wireless speaker, which will be placed near the patient's head. Delivery of the intervention to subjects randomized to receive it will begin as soon as possible during 9 am and 4 pm; if the FAVoR messages cannot be recorded before 4 pm, the intervention will begin on the following morning at 9 am. Data recording devices (SP-PSG and ActiWatch) will be applied to the subjects receiving the intervention immediately prior to the onset of the FAVoR intervention, and to control subjects as soon as feasible following consent. Actigraphy and SPPSG will continue throughout the 120-hour period beginning with the intervention delivery and continuing until the same time 5 days (120 hours) later. Data collection will resume and continue after at least 24 hours of ICU discharge. The subject will complete the NIH Toolbox-Cognition Battery, and the PROMIS Global Health instrument, and actigraphy and SP-PSG will be obtained.

We will follow University of Miami Hospital and Jackson Memorial Hospital infection control policies and procedures for cleaning portable equipment before and between patients, which include appropriate germicidal or bleach agents and single use disposable equipment covers.

As of June 2020, we will resume data collection at UMH for the following measures: CAM-ICU, Actigraphy, SP-PSG, and the NIH Toolbox Cognition Battery. Data collection remains paused for these measures at JMH.

Outpatient. There will be two outpatient data collection events at 1 month and 6 months posthospital discharge. During the 1 month home visit, research staff will travel to the subject's home (or other location agreed upon) to administer the NIH Toolbox-Cognition Battery testing and the PROMIS Global Health assessment, PROMIS-SD, PROMIS-SRI, PROMIS-CF, PROMIS-CFA questionnaires. While face-to-face interaction is not permitted, the subjects will not be asked to wear the SP-PSG and ActiWatch (for acquisition of sleep and activity data) overnight. Identical data collection processes will be used at the 6 month visit.

Procedures for telephone or video conference:

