IRB Study Number: 20170771, Version #1.8, Date: 03/10/21, PI: [name]

TBN	Research Assistant	UM SONHS [name]	[contact]
TBN	Research Assistant	UM SONHS [name]	[contact]
TBN	Research Assistant	UM SONHS [name]	[contact]
TBN	Research Assistant	UM SONHS [name]	[contact]

Conflict of Interest. None of the investigators will benefit from subjects' participation in this project or completion of the project in general.

Personnel Training. Before subjects are enrolled in the study, a comprehensive study manual will be developed describing all study procedures. Under the supervision of the PI, the Project Director will train all research assistants (RAs) on all aspects of the study, including intervention delivery, use of all study equipment (SP-PSG, actigraphy), use of the electronic medical record, and data collection and entry, documentation, and regulatory compliance. Training will include completion of the Collaborative Investigator Training Initiative (CITI) education in human subject protections. Training will continue until RAs have achieved 100% accuracy of all procedures and data collection processes, assessed by return demonstrations on all study procedures. Training reviews will occur regularly, and each RA will also be directly observed by the Project Director every 3 months throughout the study period to ensure that all critical elements of the study continue to be correctly performed. The Project Director will retrain RAs immediately if any critical element is found to be omitted or inaccurate.

19. Prior Approvals

Approval from the UMH Ancillary Committee and Jackson Health System (JHS) Clinical Research Review Committee are required.

20. Recruitment Methods

As of March 2020, to protect human subjects, we are closely following the COVID-19 safety recommendations. We have resumed enrollments at UMH as of June 2020, but continue temporarily suspending new enrollments at JMH.

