5. All consent, HIPAA, and Audio Recording forms will be collected using a secured email server.
6. The family member willing to record the scripted reorientation messages will be required to sign the Authorization for Audio Recording in Research form if recording in person. If the family member is recording by phone or Zoom, verbal consent to record will be obtained and documented by the person obtaining consent.
7. UM IRB, JMH, and UMH policies and procedures for clinical research participant enrollment and tracking will be followed.

Since this study involves continuous data collection over 120 hours, the Project Director and RAs will be involved in the pre-screening, recruitment, and enrollment of subjects, along with collection of all data. We have successfully trained RAs to pre-screen, recruit, enroll, and collect complex data processes in the ICU environment in several previous studies. Although data collection will occur continuously for 120 hours, in our experience with continuous data collection, we have found that providing support for automated data collection (for example, actigraphy) approximately 10 hours per day (i.e. 8a – 6p) in person results in collection processes which run exceptionally well in the hours when study personnel are not present. In addition, we will conduct extensive education for the unit staff about the project, although no study activities will be required from them. Study personnel will also be on call by telephone during all study hours, so that hospital staff can contact us if they have any questions about the equipment (SP-PSG and ActiWatch).

21. Local Number of Subjects

We plan to review approximately 350 medical records in order to achieve our sample size of 182 enrollments.

22. Confidentiality

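### No masking of delirium assessment is described: the staff roles that assign subjects and run FAVoR also score the CAM-ICU at message times, which leaves the primary outcome open to arm-dependent scoring

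*Combined protocol and SAP*

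**What the plan says.** All references are to the combined protocol and SAP.

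- **Assignment.** Section 9, Group Assignment: "The Project Director and Research Assistants will recruit, enroll, and assign subjects to groups".
- **Delivery and monitoring.** Section 18, Personnel Training: "the Project Director will train all research assistants (RAs) on all aspects of the study, including intervention delivery". Section 9, Description of Intervention: "Research personnel will monitor the subject and the recorded messages regularly", and they log the dose.
- **Scoring.** Section 9, Delirium: "CAM-ICU scores for each subject will be obtained by study personnel twice daily at 9 am and 4 pm". The plan sets these two times to match the first and last message of the day in the FAVoR arm, and uses the same times for controls. Scoring continues for two days after the intervention period.
- **Data collection.** Section 20, end of the enrollment process: "the Project Director and RAs will be involved in the pre-screening, recruitment, and enrollment of subjects, along with collection of all data".
- **Visible cue.** Section 9, Inpatient: "FAVoR will be delivered through a wireless speaker, which will be placed near the patient's head". Nothing comparable is described for the control group.
- **Second source.** Section 9, Delirium, also collects "documentation by providers in the medical record of episodes of delirium occurring outside of the CAM-ICU data collection". The next sentence counts a day as delirium free only if it contains no instance of delirium.

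No section that could be read describes a masked assessor, separation of delivery from assessment, concealment of the speaker, or masking of clinical staff.

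**The concern.** The CAM-ICU requires a rater's judgement, and borderline ratings can move with what the rater expects. Here the rater belongs to the team that knows the assignment. The rater is at the bedside when the first or last message of the day is due, and can see or hear which arm the subject is in. Providers who write chart notes can see the speaker too, and Section 20 says unit staff receive extensive education about the project.

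If scoring leans even modestly towards fewer positives in the FAVoR arm, the trial could report benefit where there is none. Nothing in the plan would separate that from a real effect. Section 4 promises unbiased results, and randomization alone does not protect against biased outcome assessment.

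**Working it through.** **The plan's own figure.** The documents give no figure for scoring error by arm, so there is none to reproduce. The 91 per arm (Section 8) is taken as stated; how it was derived does not affect this point. Two-sided alpha is 0.05. The shifts in sensitivity below are assumptions.

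**Inputs from the documents.** CAM-ICU sensitivity 75.5% and specificity 95.8% (Section 9, Delirium); two scores a day (same place); mean delirium duration 3.4 days (Section 9, Intervention Group); delirium in as many as 80% of ventilated patients (Section 4).

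**Assumed.** No true effect; sensitivity 10 or 20 points lower in the FAVoR arm only; independent scores; SD of delirium-free days 1.9 to 2.2; true delirium 40%, 60% or 80% in model B.

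**A. Delirium-free days (the primary outcome in Section 9).** A delirious day is missed only if both scores are negative, with probability (1 - sensitivity)².

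- Sensitivity 0.755: 0.245² = 0.060. At 0.655: 0.345² = 0.119. At 0.555: 0.445² = 0.198.
- Mean delirious days per patient: 0.80 × 3.4 = 2.72.
- Spurious gain in delirium-free days: 2.72 × (0.119 - 0.060) = 0.16 for 10 points; 2.72 × (0.198 - 0.060) = 0.375 for 20 points.
- Standard error: SD × √(2/91) = 0.282 (SD 1.9) or 0.326 (SD 2.2).
- With z = gain / standard error, the false-positive rate is Φ(z - 1.96) + Φ(-z - 1.96).

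| Sensitivity loss | SD 1.9 | SD 2.2 |
|---|---|---|
| none | 5% | 5% |
| 10 points | z = 0.57, 8.8% | z = 0.49, 7.8% |
| 20 points | z = 1.33, 26.6% | z = 1.15, 21.0% |

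These figures move with the number of delirious days. A simulation averaging 3.5 such days over the seven scored days gave 11% for 10 points and 40% for 20 points.

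**B. One decisive score per patient (closer to the 2x2 chi-square in the Data Analysis Plan).** Observed rate = true rate × sensitivity + (1 - true rate) × 0.042. At 80% true delirium this is 0.8 × 0.755 + 0.2 × 0.042 = 0.612 in controls and 0.8 × 0.655 + 0.2 × 0.042 = 0.532 in the FAVoR arm, a spurious difference of 8 percentage points. A two-proportion test with 91 per arm gives:

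| True delirium | 10-point loss | 20-point loss |
|---|---|---|
| 40% | 9% | 22% |
| 60% | 13% | 38% |
| 80% | 19% | 58% |

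With no difference between arms in scoring, both models return 5%.

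**The case against.** Several parts of the other side's case stand.

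- **Overlap is by role.** A reader might infer that one person assigns, delivers and scores for a given subject. No section says so, though none prevents it. Playback is automated once set up. The plan is silent on masking, so calling the scorers unmasked is an inference, though a strong one.
- **Small shifts do not settle the result.** A reader might move the proportion ever delirious straight down from 80%. With 91 per arm, shifts of 5, 10 and 15 points then give rejection rates of 13%, 34% and 62%. That overstates the case. Even there, a 5-point shift yields no significant result 87% of the time. With about seven scores over 3.4 delirious days, turning a patient from ever to never delirious means missing all of them. A 10-point sensitivity loss moves that proportion by only 0.8 × (0.345⁷ - 0.245⁷), under 0.1 percentage point if scores are independent.
- **Chart notes cut both ways.** The counting rule does not name its sources; that chart entries count is read from the adjacent sentence. A provider note can also restore a delirious day that research staff missed.
- **Quality controls exist.** Assistants are trained to 100% accuracy and observed every 3 months, with quarterly fidelity checks (Sections 11 and 18). These limit drift but do not address knowledge of arm.
- **Staffing is uncertain.** The legible part of the personnel list shows four research assistant posts, all to be named, for two hospitals. It does not show that two assistants are on site at each scoring time, so a strict rota without added staff is unproven.

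The general reply that a behavioural intervention cannot be masked applies to subjects and deliverers. It does not explain why scoring must coincide with messages, or why the scorer may be the person monitoring them.

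**Conclusion.** The point holds as a design weakness that should be reduced. As written, the plan lets staff who know the arm judge the primary outcome at message times, and nothing in it limits or measures the effect. It raises the chance of a false-positive result without making one likely at small shifts.

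For an assumed 10-point loss of sensitivity in one arm, the false-positive rate rises from 5% to about 8-9% on delirium-free days, or 9-19% if one score decides each patient. For 20 points it is about 21-27%, or 22-58%. These ranges rest on no true effect, 91 per arm, independent scores, SD 1.9-2.2 and 2.72 delirious days per patient for the first range, and 40-80% true delirium for the second. The documents do not say whether any such loss occurs, or how large it would be.

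They do not support the claim that bias will produce a significant result, or that the same individual fills every role.

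**What to change.** 1. In Section 9, Delirium, state that the CAM-ICU is scored when no message is playing, before the 9 am message and after the 4 pm message ends, at the same times in both arms.
2. Place one of the speakers already obtained (Section 7), silent, at control bedsides. The number of speakers is not given; at most four subjects are active at once.
3. Where the existing roster allows, have the CAM-ICU scored by an assistant who did not assign that subject or record or monitor that subject's messages. Record who scored each assessment.
4. State explicitly whether chart entries count towards delirium-free days. Report the outcome on research CAM-ICU alone as a sensitivity analysis beside the any-source definition. Table 1 already lists the two sources separately. This shows how much of the result depends on chart notes. A reader might take agreement between the two as proof of unbiased scoring, but both contain the same CAM-ICU scores, so it is not.

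**Cost.** Rota planning and one extra analysis; these steps, with item 3 limited to the existing roster, need no new staff. Masking stays partial, because controls hear no messages and the team is small. At version 1.8, with enrollment already under way, items 1 to 3 change measurement conditions for later subjects, so report results before and after the change. Item 4 can use the data already collected on earlier subjects.
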